3.1.2. Laboratory Data

Safety laboratory tests will be performed as described in the protocol. See Protocol Appendix 2 for the list of clinical safety laboratory tests to be performed.

To determine if there are any clinically significant laboratory abnormalities, the hematological, clinical chemistry (serum) and urinalysis safety tests will be assessed against the criteria specified in the sponsor reporting standards. The assessment will not take into account whether each subject's baseline test result is within or outside the laboratory reference range for the particular laboratory parameter.

Baseline of safety laboratory tests is defined as the pre-dose measurement on Day -1. If a value is missing on Day -1, then the last pre-dose measurement will be used as baseline.

3.1.3. Vital Signs

Supine blood pressure and pulse rate measurements will be taken at all time points listed in the SoA given in the protocol.

The baseline measurement is the pre-dose measurement at Hour 0 taken on Day 1. If a value is missing on Day 1, then the last pre-dose measurement will be used as baseline.

3.1.4. ECG

Triplicate 12-lead ECGs will be obtained approximately 2 to 4 minutes apart; the average of the triplicate ECG measurements collected before dose administration on Day 1 will serve as each participant's time-controlled baseline QTcF value. If a value is missing on Day 1, then the last pre-dose measurement will be used as baseline.

The QT, QTc, PR, QRS and heart rate will be recorded at each assessment time.

If not supplied, QTcF will be derived using Fridericia's heart rate correction formula:

 $QTcF = QT/(RR)^{1/3}$ where RR = 60/HR (if not provided)

3.2. Secondary Endpoint(s): PK Parameters

• Plasma PK of multiple topical doses of PF-07295324 and PF-07259955, as data permits:

Day 1: Cmax, Tmax, Cavg, Ctrough, AUCtau

Day 10: Cmax, Tmax, Cavg, Ctrough, AUCtau, Rac (Cmax), Rac(AUCtau), t1/2, CL/F, and Vz/F

Actual PK sampling times will be used in the derivation of PK parameters.

PK parameters for PF-07295324 and PF-07259955, following topical administration, will be derived from the plasma concentration-time profiles using non-compartmental methods, as data permit.

The PK parameters to be assessed in this study, their definition, and method of determination are listed in Table 2. Actual PK sampling times will be used in the derivation of PK parameters.

Parameter Day		Definition	Method of Determination	
C _{max}	1, 10	Maximum plasma concentration	Observed directly from data	
T _{max}	1, 10	Time at which maximum plasma concentration occurs	Observed directly from data	
Cavg	1, 10	Average plasma concentration	AUC _{tau} /tau; where tau is the dosing interval and AUC _{tau} is area under the plasma concentration-time profile from time zero to time tau (τ) , the dosing interval	
C _{trough}	1, 5, 7 and 10	Pre-dose Concentration	Observed directly from data	
$t_{\nu_2}^{a}$	10	Terminal half-life	$Log_e(2)/k_{el}$, where k_{el} is the terminal phase rate constant calculated by a linear regression of the log-linear concentration-time curve	
AUC _{tau}	1, 10	Area under the plasma concentration-time profile from time zero to time tau (τ) , the dosing interval	Linear/Log trapezoidal method up to tau, the dosing interval	
CL/F	10	Apparent clearance	Dose/AUC _{tau}	
V _z /F ^a	10	Apparent volume of distribution	$Dose/(AUC_{tau} \times k_{el})$	
$R_{ac}\left(C_{max} ight)$	10	Accumulation ratio for C _{max}	C _{max, Day 10} /C _{max, (first dose)}	
R _{ac} (AUC _{tau})	10	Accumulation ratio for AUC _{tau}	AUC _{tau, Day 10} /AUC _{tau, (first dose)}	

a. as data permit.

4. ANALYSIS SETS (POPULATIONS FOR ANALYSIS)

Data for all participants will be assessed to determine if participants meet the criteria for inclusion in each analysis population prior to unblinding and releasing the database and classifications will be documented per standard operating procedures.

Population	Description
Enrolled	All participants who sign the ICD.
Randomly assigned to investigational product	All participants who sign the ICD and determined eligible to participate in the study.
Evaluable	The evaluable population is defined as all participants who are randomly assigned to IP and who are applied at least 1 dose of IP.
Safety	All participants randomly assigned to IP and who are applied at least 1 dose of IP. Participants will be analyzed according to the product they actually received.
PK concentration	All participants randomly assigned to investigational product who received an application of PF-07295324 or PF-07259955 and in whom at least 1 plasma sample concentration value is reported.
PK parameter	All participants randomly assigned to investigational product who received an application of PF-07295324 or PF-07259955 and who have at least 1 of the PK parameters of interest calculated.

4.1. Treatment Misallocations

All analyses will be performed on an "as-treated" basis and will not include data from participants who are randomized but not treated.

If a participant takes a treatment that is not consistent with the treatment they are randomized to, for example takes a treatment out of sequence or takes the same treatment twice, then they will be reported under the treatment that they actually receive for all safety, PK and pharmacodynamic analyses, where applicable.

4.2. Protocol Deviations

Participants who experience events that may affect their PK profile may be excluded from the PK analysis. At the discretion of the pharmacokineticist, a concentration value may also be excluded if the deviation in sampling time is of sufficient concern or if the concentration is anomalous for any other reason.

A full list of protocol deviations will be compiled and reviewed to identify major and minor deviations prior to database closure.

5. GENERAL METHODOLOGY AND CONVENTIONS

5.1. Hypotheses and Decision Rules

No formal hypothesis testing will be performed in this study.

5.2. General Methods

Descriptive analyses will be performed. Some measures will be summarized using graphical representations, where appropriate.

5.2.1. Analyses for Continuous Endpoints

For continuous variables, the data will be summarized using the number of subjects, mean, median, standard deviation, minimum, and maximum in accordance with current Pfizer's data and reporting standards. For appropriate PK parameters, geometric mean and geometric coefficient of variation (geocv%) will also be summarized.

5.2.2. Analyses for Categorical Endpoints

For categorical or ordinal variables, number of subjects, numbers and percentages of subjects meeting the categorical criteria will be supplied in accordance with current Pfizer's data and reporting standards.

5.3. Methods to Manage Missing Data

For the analysis of safety endpoints, the sponsor data standard rules for imputation will be applied.

Methods to handle missing PK data are described below.

Concentrations Below the Limit of Quantification:

In all data presentations (except listings), concentrations below the limit of quantification (BLQ) will be set to zero. (In listings BLQ values will be reported as "<LLQ" where LLQ will be replaced with the value for the lower limit of quantification).

Deviations, Missing Concentrations and Anomalous Values:

In summary tables and plots of median profiles, statistics will be calculated having set concentrations to missing if 1 of the following cases is true:

- 1. A concentration has been collected as ND (ie, not done) or NS (ie, no sample),
- 2. A deviation in sampling time is of sufficient concern or a concentration has been flagged anomalous by the pharmacokineticist.

Note that summary statistics will not be presented at a particular time point if more than 50% of the data are missing.

Pharmacokinetic Parameters:

Actual PK sampling times will be used in the derivation of PK parameters. If a PK parameter cannot be derived from a subject's concentration data, the parameter will be coded as NC (ie, not calculated). (Note that NC values will not be generated beyond the day that a subject discontinues). In summary tables, statistics will be calculated by setting NC values to

missing; and statistics will be presented for a particular dose with \geq 3 evaluable measurements.

If an individual subject has a known biased estimate of a PK parameter (due for example to an unexpected event such as vomiting before all the compound is adequately absorbed from the gastrointestinal tract), this will be footnoted in summary tables and will not be included in the calculation of summary statistics or statistical analyses.

6. ANALYSES AND SUMMARIES

6.1. Primary Endpoint(s)

6.1.1. Safety Summaries and Analyses

All safety analyses will be performed on the safety population (See Section 4).

AEs, ECGs, BP, pulse rate, skin irritation assessment, and safety laboratory data will be reviewed and summarized on an ongoing basis during the study, to evaluate the safety of participants. Any clinical laboratory, ECG, BP, and pulse rate abnormalities of potential clinical concern will be described. Safety data will be presented in tabular and/or graphical format and summarized descriptively, where appropriate.

Medical history and physical examination and neurological examination information, as applicable, collected during the course of the study will be considered as source data and will not be required to be reported, unless otherwise noted. However, any untoward findings identified on physical and/or neurological examinations conducted during the active collection period will be captured as AEs, if those findings meet the definition of an AE. Data collected at screening that are used for inclusion/exclusion criteria, such as laboratory data, ECGs, and vital signs, will be considered source data, and will not be required to be reported, unless otherwise noted. Demographic data collected at screening will be reported.

PF-07295324 and PF-07259955 will have corresponding vehicle groups throughout, ie, vehicle groups will be summarized by administration type (ointment and cream).

6.1.1.1. Adverse Events

Adverse events will be reported in accordance with the sponsor reporting standards.

Subject discontinuations due to adverse events will be detailed by treatment. Data will be reported in accordance with sponsor reporting standards.

Skin irritation assessment using Draize Score will be listed and summarized by treatment.

6.1.1.2. Laboratory Data

Laboratory data will be listed and summarized by treatment in accordance with the sponsor reporting standards.

6.1.1.3. Vital Signs

Single supine blood pressure and pulse will be collected at times specified in the SoA in the protocol.

The following vital signs endpoints will be determined and summarized for each treatment group:

- Actual values, change from baseline in supine blood pressure and pulse rate over all measurements taken postdose;
- The maximum decrease and increase from baseline over all measurements taken postdose for supine blood pressure.

The increase from baseline will be calculated by subtracting the baseline value from each post-dose measurement to give the change from baseline for each participant. The maximum of these values over the duration of dosing will be reported as maximum increase from baseline, except where a participant does not show an increase. In such an instance, the minimum decrease will be reported.

Similarly, decrease from baseline will be calculated by subtracting each post-dose measurement from individual participant's baseline value. Maximum decrease from baseline will be reported as the minimum value of the changes from baseline. In cases where a participant does not show a decrease, the minimum increase will be reported.

Maximum absolute values and changes from baseline for vital signs will also be tabulated by treatment using categories as defined in Appendix.

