3. ENDPOINTS AND BASELINE VARIABLES: DEFINITIONS AND CONVENTIONS

3.1. Primary Endpoint(s): Safety Endpoints

- Incidence and severity of systemic AEs, safety laboratory tests, vital signs (including blood pressure and pulse rate), and heart rhythms as assessed via 12-lead electrocardiogram (ECG).
- Incidence and severity of application site AEs as assessed by Draize score.

The following data are considered in standard safety summaries (see protocol for collection days, baseline assessment, and list of parameters):

- AEs;
- Safety laboratory tests;
- Vital signs (Blood Pressure and Pulse rate);
- ECG.

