8. APPENDICES

Appendix 1. Categorical Classes for ECG and Vital Signs of Potential Clinical Concern

Categories for QTcF

Degree of Prolongation	Mild (msec)	Moderate (msec)	Severe (msec)
Absolute value	>450-480	>480-500	>500
Increase from baseline		30-60	>60

Categories for PR and QRS

PR (ms)	max. ≥300	
PR (ms) increase from baseline	Baseline >200 and max. ≥25% increase	Baseline ≤200 and max. ≥50% increase
QRS (ms)	max. ≥140	
QRS (ms) increase from baseline	≥50% increase	

Categories for Vital Signs

Systolic BP (mm Hg)	min. <90	
Systolic BP (mm Hg) change from baseline	max. decrease ≥30	max. increase ≥30
Diastolic BP (mm Hg)	min. <50	
Diastolic BP (mm Hg) change from baseline	max. decrease ≥20	max. increase ≥20
Supine pulse rate (bpm)	min. <40	max. >120

Measurements that fulfill these criteria are to be listed in the clinical study report.

Abbreviation	Term
Abs	absolute
AD	atopic dermatitis
ADL	activities of daily living
AE	adverse event
ALT	alanine aminotransferase
AST	aspartate aminotransferase
AUC	area under the curve
AUC ₂₄	area under the plasma concentration-time curve from 0 to 24 hours
AUC _{tau}	Area under the plasma concentration-time profile from time zero to
	time tau (τ), the dosing interval
AV	atrioventricular
BBS	Biospecimen Banking System
BID	twice daily
BLQ	below the limit of quantification
BMI	body mass index
BP	blood pressure
bpm	beats per minute
BSA	body surface area
BUN	blood urea nitrogen
BW	body weight
Cav/Cavg	average concentration
Ctrough	pre-dose Concentration
CCL26	chemokine (C-C motif) ligand 26
CFR	Code of Federal Regulations
CIOMS	Council for International Organizations of Medical Sciences
СК	creatine kinase
CLp	clearance of the drug from plasma
CL/F	apparent clearance
C _{max}	maximum observed concentration
CO ₂	carbon dioxide (bicarbonate)
Coh	cohort
COVID-19	coronavirus disease 2019
CRF	case report form
CRO	contract research organization
CRU	clinical research unit
CSR	clinical study report
CXCL10	C-X-C motif chemokine 10
СҮР	cytochrome P450

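### SAP 6.1.1.3 names the wrong statistic, mixes two sign conventions and gives two windows for vital-sign extremes, so category tables programmed literally would disagree with the CSR listing

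*SAP*

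**What the plan says.** SAP 3.1 places blood pressure and pulse rate in the primary safety endpoint. SAP 3.1.3 fixes the reference value: "The baseline measurement is the pre-dose measurement at Hour 0 taken on Day 1". SAP 6.1.1.3 then gives these rules.

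- **Increase.** It is found by "subtracting the baseline value from each post-dose measurement to give the change from baseline for each participant". The SAP continues: "The maximum of these values over the duration of dosing will be reported as maximum increase from baseline". A participant with no rise has the smallest decrease reported instead.
- **Decrease.** The SAP states that "decrease from baseline will be calculated by subtracting each post-dose measurement from individual participant's baseline value", and then: "Maximum decrease from baseline will be reported as the minimum value of the changes from baseline". A participant with no fall has the smallest increase reported instead.
- **Window.** A bullet earlier in the section sets both extremes for supine blood pressure over every post-dose measurement.
- **Categories.** "Maximum absolute values and changes from baseline for vital signs will also be tabulated by treatment using categories as defined in Appendix".

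The absolute criteria in SAP Appendix 1 are minimum systolic <90, minimum diastolic <50, minimum pulse <40 and maximum pulse >120. The systolic change criteria are "max. decrease ≥30" and a maximum increase of at least 30; the diastolic ones are 20 in each direction. Appendix 1 also requires measurements that meet a criterion to be listed in the CSR.

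**The concern.** The section tells the programmer to tabulate one statistic while the appendix is labelled for another. It defines a decrease with one sign and extracts its maximum with the other. It also describes the period for the maximum increase in two ways. Each conflict has to be settled by guessing intent.

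At stake are the by-treatment category tables, which set active beside vehicle for blood-pressure and pulse extremes. With 4 active participants per cohort, one misclassified active participant moves a cohort's active-group percentage by 1/4 = 25 points. A table that shows no low values beside a listing that shows some would also need explaining in the CSR.

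**Working it through.** The plan gives no figure to reproduce here: the study is descriptive, with no hypothesis test behind these tables. The check applies the written rules to assumed readings and counts scheduled times. All blood-pressure values below are illustrative assumptions, not figures from the documents.

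**1. Absolute values.** Assume baseline systolic 120 and post-dose 118, 85, 110, 125, 121.

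- Statistic named in 6.1.1.3: maximum = 125. Is 125 < 90? No, so not counted.
- Statistic named in Appendix 1: minimum = 85. Is 85 < 90? Yes, so counted.

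Under the literal rule a participant enters the low systolic row only if every post-dose reading is below 90. The same holds for diastolic <50 and pulse <40. Of the four absolute criteria, only pulse >120 uses a maximum.

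**2. Sign of the decrease.** Same participant.

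| Quantity | Values | Extreme | Is it ≥30? |
|---|---|---|---|
| Change = post − baseline | −2, −35, −10, +5, +1 | minimum = −35 | no, as a signed number |
| Decrease = baseline − post | 2, 35, 10, −5, −1 | maximum = 35 | yes |
| Decrease = baseline − post | as above | minimum = −5 | no |

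The third row would be the wrong reading of the person's data. The SAP's text does not lead there, because it takes the minimum of the changes, and it has just defined change as post-dose minus baseline. The fallback confirms this. Take a participant with rises only (baseline 120, post-dose 122, 130, 125):

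- minimum of (post − baseline) = +2, which is the smallest increase, as the SAP says;
- minimum of (baseline − post) = −10, which is the largest increase with its sign reversed, and contradicts the SAP.

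So the rule selects the correct fall but carries it as −35, and −35 ≥ 30 is false. Compared literally, the minimum change reaches +30 only when every post-dose reading has risen by at least 30, which is not a fall at all.

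**3. Window for the maximum increase.** Scheduled post-dose vital signs, from protocol Tables 1 and 2 and the footnotes to Table 1:

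- Day 1 at 1, 4, 8 and 12 h: 4
- Days 2, 5 and 7 before the morning application, and Day 10 at 0 h: 4
- Day 10 at 1, 4, 8 and 12 h: 4
- Days 11 and 12: 2

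Total = 4 + 4 + 4 + 2 = 14. The SAP does not say when the duration of dosing ends.

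| End of dosing taken as | Readings used | Readings left out |
|---|---|---|
| Last application, Day 10 morning | 8 of 14 | 6 (43%) |
| 12 h after the last application | 12 of 14 | 2 (14%) |
| All post-dose measurements | 14 of 14 | 0 |

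The restriction is attached only to the increase. The decrease keeps all 14.

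**The case against.** The strongest reply is that the intent is clear and nothing would be lost. Appendix 1 labels each row as a minimum or a maximum. A change of −35 is plainly a decrease of 35, and the SAP's own decrease formula returns +35. Measurements meeting a criterion are listed one by one, so a systolic value of 85 appears however the table is built. SAP 5.2.1 requires minimum and maximum in summaries of continuous variables, and 6.1.1.3 summarises actual values and changes. SAP 6.1.1 has abnormalities of potential clinical concern described. With about 6 participants per cohort, such a value would be easy to see.

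Most of this stands, and it rules out several stronger readings that a reader might infer:

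- That the SAP takes the minimum of baseline minus post-dose. The definition of change and the fallback sentence fit only post-dose minus baseline.
- That blood-pressure falls would go unnoticed. The listing, summaries and descriptions would still show them.
- That the window hides falls. It is written for increases only.
- That Appendix 1 holds the only pre-set flag for bradycardia. Protocol Appendix 7 also lists a rate below 40 bpm.

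The reply does not rescue the tables. Naming the maximum where a minimum is needed, and leaving a sign reversal and an end of window unstated, still leaves rules that give wrong counts when followed as written.

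**Conclusion.** The point holds as a minor defect: three wording errors that would make the vital-sign category tables wrong, and out of step with the CSR listing, if programmed literally. The absolute-value error is the clearest and would leave the low blood-pressure and low-pulse rows near empty. The sign error picks the right reading but cannot meet the decrease thresholds as a signed number. The window error could leave 2 to 6 of 14 scheduled readings out of the maximum increase.

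This rests on literal programming of 6.1.1.3; a programmer who infers intent from Appendix 1 would avoid the first two errors. The reading counts assume the protocol schedule with no unscheduled or missed measurements. No rate of misclassified participants is given, because the documents state no within-participant variability for blood pressure. A claim that falls would be missed is not supported.

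**What to change.** Amend SAP 6.1.1.3 as follows.

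- Define change as post-dose minus baseline throughout.
- Define maximum increase as the largest change. Define maximum decrease as the largest value of baseline minus post-dose, carried as a positive number into the ≥30 and ≥20 criteria. A negative result then means that no fall occurred.
- Tabulate minimum post-dose values for the Appendix 1 categories marked 'min.' and maximum values for those marked 'max.'.
- Use one window for both extremes: all post-dose measurements through Day 12 or early termination.

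The cost is a few sentences of SAP text before programming. It needs no new data and no change to the assessments.

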6.1.1.4. ECG

Changes from baseline for the ECG parameters QT interval, heart rate, QTc interval, PR interval, and QRS complex will be summarized by treatment and time.

The maximum absolute value (post-dose) and the maximum increase from baseline for QTcF, QT, heart rate, PR and QRS, will be determined over all measurements taken post-dose and reported.

The number (%) of participants with maximum postdose QTc values and maximum increases from baseline in the following categories will be tabulated by treatment:

Degree of Prolongation	Mild (msec)	Moderate (msec)	Severe (msec)
Absolute value	>450-480	>480-500	>500
Increase from baseline		30-60	>60

Safety QTc Assessment

In addition, the number of participants with uncorrected QT values >500 msec will be summarized.

If more than 1 ECG is collected at a nominal time after dose administration (for example, triplicate ECGs), the mean of the replicate measurements will be used to represent a single observation at that time point. If any of the 3 individual ECG tracings has a QTc value >500 msec, but the mean of the triplicates is not >500 msec, the data from the participant's individual tracing will be described in a safety section of the clinical study report (CSR) in order to place the >500-msec value in appropriate clinical context. However, values from individual tracings within triplicate measurements that are >500 msec will not be included in the categorical analysis unless the average from the triplicate measurements is also >500 msec. Changes from baseline will be defined as the change between the postdose QTc value and the average of the time-matched baseline triplicate values on Day -1, or the average of the predose triplicate values on Day 1.

